7.7.1 PK Parameters

All individual PK parameters will be listed for BMS-986004 including any exclusions and reasons for exclusion from summaries. Summary statistics will be tabulated for each PK parameters by treatment and by study day. Geometric means and coefficients of variation will be presented for C_{max}, AUC(TAU), CLT, AI_AUC, and AI_C_{max}. Decimal place specifications for summary statistics are described in [Section 7.11](#).

PK parameters will be summarized for day 1 and day 71 with the grouping decided by current dose - the planned dose on each of the two study days, as subjects are expected to have achieved steady state by day 71. Under this assumption, the PK parameters are considered to be related to the current dose, regardless of the previous doses. As such, 75mg dose group on day 71 consists of subjects dosed at 75mg only; 225mg dose group on day 71 consists of subjects from both non-responders of 75mg cohort and responders of 225mg cohort, all of whom will be dosed at 225mg; 675mg dose group on day 71 consists of subjects from both non-responders of 225mg cohort and responders of 675mg cohort; 1500mg dose group on day 71 consists all of the subjects from 1500mg cohort and also the non-responders from 675mg.

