- h) The following clinical chemistries MUST NOT exceed 2 times the normal reference range: ALT, AST, alkaline phosphatase, and bilirubin >1.5 times upper limit normal (ULN) (isolated bilirubin $>1.5 \times \text{ULN}$ is acceptable if bilirubin is fractionated and direct bilirubin is $<35\%$)
- i) Albumin must be within 80 to 120% of normal range

3. Age and Reproductive Status

- a) Males and Females, ≥ 18 years old.
- b) Women of childbearing potential (WOCBP) must have a negative serum or urine pregnancy test (minimum sensitivity 25 IU/L or equivalent units of HCG) within 24 hours prior to the start of study drug.
- c) Women must not be breastfeeding
- d) WOCBP must agree to follow instructions for method(s) of contraception for the duration of treatment with study drug (84 days) plus 5 half-lives of study drug (20 days) plus 30 days (duration of ovulatory cycle) for a total of 134 days post-treatment completion.
- e) Males who are sexually active with WOCBP must agree to follow instructions for method(s) of contraception for the duration of treatment with study drug (84 days) plus 5 half-lives of the study drug (20 days) plus 90 days (duration of sperm turnover) for a total of 194 days post-treatment completion.
- f) Azoospermic males and WOCBP who are continuously not heterosexually active are exempt from contraceptive requirements. However they must still undergo pregnancy testing as described in this section.

Investigators shall counsel WOCBP and male subjects who are sexually active with WOCBP on the importance of pregnancy prevention and the implications of an unexpected pregnancy. Investigators shall advise WOCBP and male subjects who are sexually active with WOCBP on the use of highly effective methods of contraception. Highly effective methods of contraception have a failure rate of $< 1\%$ when used consistently and correctly.

At a minimum, subjects must agree to the use of one method of highly effective contraception as listed below:

HIGHLY EFFECTIVE METHODS OF CONTRACEPTION

- Male condoms with spermicide
- Hormonal methods of contraception including combined oral contraceptive pills, vaginal ring, injectables, implants and intrauterine devices (IUDs) such as Mirena® by WOCBP subject or male subject's WOCBP partner. Female partners of male subjects participating in the study may use hormone based contraceptives as one of the acceptable methods of contraception since they will not be receiving study drug
- IUDs, such as ParaGard®

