4.3 Pharmacokinetic Endpoints

Pharmacokinetic parameters of BMS-986004 will be derived from serum concentration versus time data by analyte and collection interval. Individual pharmacokinetic parameter values will be derived by non-compartmental methods by a validated pharmacokinetic analysis program using actual times.

Table 4.3-1: Commonly Used PK Parameters, Naming Conventions and Definitions

Parameter	Definition
Cmax	Maximum observed serum concentration
AUC(TAU)	Area under the concentration time curve in one dosing interval
Ctrough	Trough observed concentration
CLT	Total body clearance
AI_AUC	AUC Accumulation Index; ratio of AUC(TAU) at steady state to AUC(TAU) after the first dose
AI_Cmax	Cmax Accumulation Index; ratio of Cmax at steady-state to Cmax after the first dose

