6.2 Treatment Groups

Treatment groups will be decided by the planned starting dose regardless of intra-subject dose escalation planned at day 57. Table 6.2-1 below indicates the planned treatment groups.

All summaries, except PK summary, will be provided by treatment group. For PK summary, it is current dose that is used to decide the dose group.

Table 6.2-1: Treatment Group

Cohort	Treatment Group Label
A	BMS 75mg
B	BMS 225mg
C	BMS 675mg
D	BMS 1500mg

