7.7 Pharmacokinetics

PK sampling date and time are shown below in [Table 7.7-1](#) for convenience. On day 57, non-responders in each treatment group other than the 1500mg group will be dose-escalated to the starting dose of the next higher treatment group.

The Pharmacokinetic (PK) population will be used for all listings. Evaluable PK population will be used for summaries. PK parameters and C_{trough} will be summarized for each group decided by current dose, and dose proportionality analysis will be provided by excluding subjects who have dose escalation on day 57.

Table 7.7-1: PK Sample Study Day and Time

study day	dosing	PK Sampling
1	#1, at starting dose	0h, 2h, 24h, 72h, 168h
15	#2, at starting dose	0h
29	#3, at starting dose	0h
43	#4, at starting dose	0h, 168h
57	#5, Responder: at starting dose Non-Responder: at titration dose	0h, 2h
71	#6, at the same dose as Day 57	0h, 2h, 24h, 96h, 168h
85	#7, at the same dose as Day 57	0h, 336h, 672h

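### The accumulation indices have no dose term, yet they are summarised by current dose with escalated subjects pooled in, so the planned dose step is counted as accumulation

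*SAP*

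**What the plan says.** **Definition.** SAP 4.3 (Table 4.3-1) and Protocol 5.5 and 8.3.2 define AI_AUC as "AUC Accumulation Index; ratio of AUC(TAU) at steady state to AUC(TAU) after the first dose". AI_Cmax is defined in the same way. Neither has a dose term. Protocol 8.3.2 lists both as secondary PK endpoints.

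**Grouping.** SAP 6.2 sets the general rule: "For PK summary, it is current dose that is used to decide the dose group". SAP 7.7 repeats that PK parameters "will be summarized for each group decided by current dose", and SAP 7.7.1 says "PK parameters will be summarized for day 1 and day 71 with the grouping decided by current dose". The reason given in 7.7.1 is that subjects should be at steady state by Day 71, so that earlier doses no longer matter.

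**Pooling.** SAP 7.7.1 states that the "225mg dose group on day 71 consists of subjects from both non-responders of 75mg cohort and responders of 225mg cohort". The 675 and 1500 mg groups are built the same way; the 75 mg group contains only subjects who stayed on 75 mg. AI_AUC and AI_Cmax are both named in 7.7.1 among the parameters to be given as geometric mean and CV.

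**Exclusion.** SAP 7.7 and 7.7.3 remove escalated subjects from the Day 71 power model. No other visible rule mentions them.

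**The concern.** The steady-state argument in 7.7.1 suits Cmax, AUC(TAU) and CLT measured on Day 71, because each belongs to one dose. It does not suit a ratio whose numerator is measured at the escalated dose and whose denominator was measured on Day 1 at the lower starting dose. For an escalated subject that ratio is the accumulation multiplied, nearly, by the dose step.

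No other sampling day avoids this. In SAP Table 7.7-1, doses 2 to 4 have only pre-dose samples, plus one 168 h sample after dose 4. Dose 5 (Day 57) is already at the new level, and dose 6 (Day 71) is given "at the same dose as Day 57". The only full profiles are on Days 1 and 71, which matches doses 1 and 6 in Protocol 8.4.4.

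At stake is the summary of two listed secondary endpoints. Under current-dose grouping the 75 mg group is clean and the three higher groups are inflated. A reader could take this for dose-dependent accumulation.

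**Working it through.** The documents state no expected accumulation index, so there is no plan figure to reproduce.

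**Inputs**
- Doses 75, 225, 675 and 1500 mg, 10 subjects per cohort, every 14 days (SAP 2.1). Steps: 225/75 = 3; 675/225 = 3; 1500/675 = 2.222.
- Half-life: Protocol 3.3.1 counts "plus 5 half-lives of study drug (20 days) plus 30 days (duration of ovulatory cycle", so 20/5 = 4 days.
- Share not escalated: the Appendix 2 response rates 0.20, 0.40 and 0.55 at 75, 225 and 675 mg. This is a stand-in, because escalation uses the 50,000/mm³ criterion (Protocol 3.1.1). SAP 7.7.3 expects 20% to 50%, used as a sensitivity range.
- Assumption: linear one-compartment PK.

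**Per-subject index at dose 6.** The fraction remaining after one interval is e = 2^(−14/4) = 0.0884.
- Same dose throughout: 1 + e + e² + e³ + e⁴ + e⁵ = 1.097.
- Escalated (doses 5 and 6 at the new level): step × (1 + e) + e² + e³ + e⁴ + e⁵ = 3.274 for step 3 and 2.427 for step 2.222.
- Inflation factor per escalated subject: 3.274/1.097 = 2.984; 2.427/1.097 = 2.213.

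**Pooled geometric mean.** Inflation = factor^(escalated share); reported index = inflation × 1.097, the value that would be correct in every row.

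| Day 71 group | Escalated / total | Inflation | Reported index |
|---|---|---|---|
| 75 mg | 0 / 2 | 1 | 1.10 |
| 225 mg | 8 / 12 | 2.07 | 2.27 |
| 675 mg | 6 / 11.5 | 1.77 | 1.94 |
| 1500 mg | 4.5 / 14.5 | 1.28 | 1.40 |

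The bare dose step gives almost the same inflation, so the half-life hardly matters here: 3^(8/12) = 2.08, 3^(6/11.5) = 1.77, 2.222^(4.5/14.5) = 1.28.

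**Chance variation.** With responder counts drawn as Bin(10, 0.20), Bin(10, 0.40) and Bin(10, 0.55) in 200,000 draws, the 5th to 95th percentiles of the reported index are 1.97–2.73, 1.63–2.36 and 1.25–1.52 at 225, 675 and 1500 mg. These cover binomial variation only, not uncertainty about the rates.

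**SAP range of 20% to 50% (bare step, common rate)**
- 225 and 675 mg: 3^0.8 = 2.41 down to 3^0.5 = 1.73.
- 1500 mg: 2.222^(8/18) = 1.43 down to 2.222^(5/15) = 1.30.

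**Added spread.** With escalated share s, mixing alone gives a geometric CV of √(exp(ln(step)² · s(1 − s)) − 1), or 55%, 59% and 38% at 225, 675 and 1500 mg.

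**Grouping by starting dose instead.** Inflation is 2.984^0.8 = 2.40, 2.984^0.6 = 1.93 and 2.213^0.45 = 1.43 at 75, 225 and 675 mg. The artefact moves to other groups and remains.

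**Dose-normalising.** Dividing an escalated subject's index by the step gives 3.274/3 = 1.091 and 2.427/2.222 = 1.092, against 1.097. Longer half-lives, assumed for sensitivity, give 1.28–1.29 against 1.33 (7 days) and 1.66–1.71 against 1.97 (14 days).

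**The case against.** The strongest reply is that the SAP never says which day's dose assigns a two-day ratio to a group, so the pattern with 75 mg clean and the higher doses inflated is one reading of it. That is fair as to which groups are hit. It does not remove the error, because starting-dose grouping inflates 75, 225 and 675 mg instead. Current-dose grouping is also the rule that SAP 6.2 sets for PK summaries generally.

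Second, summaries are limited to subjects with adequate profiles (SAP 6.3, not further defined in the visible text). SAP 7.11.2 defers exclusions to a sponsor PK document and allows single parameters to be dropped, and table details are left to the data presentation plan (SAP 8). Those documents are not available and may already deal with the matter. The visible text does not: none of its exclusion rules mentions escalation.

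Third, the group figures rest on a proxy for the escalation share, a half-life inferred from contraception wording, and linear PK. That stands, and the group values are illustrative. The per-subject step of 3 or 2.22 follows from the planned doses alone, although adaptive dose selection could change it.

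Fourth, the consequence is modest. The indices are descriptive, no test or escalation rule uses them, individual values are listed, and Day 71 Cmax, AUC(TAU) and CLT are not distorted in this way if steady state holds. This limits the severity but does not make the planned summary correct.

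**Conclusion.** The concern holds. Followed as written, the SAP counts a planned 3-fold or 2.22-fold dose increase as drug accumulation in every escalated subject. Under the stated assumptions the group geometric means are inflated about 2.1-, 1.8- and 1.3-fold at 225, 675 and 1500 mg. The direction depends on neither the half-life nor the response rate: any escalated subject raises the index of the group in which that subject is counted. The size in each group does depend on the escalation share, which is not known in advance. The point should be fixed before the analysis, but its consequence is minor to moderate. Confidence is medium, because the sponsor's PK document and the data presentation plan could not be checked.

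**What to change.** In SAP 4.3 and 7.7.1, state one of the following:

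1. AI_AUC and AI_Cmax are summarised only in subjects who received the same dose on Day 1 and Day 71, with escalated subjects' values listed. This is the sounder option. Its cost is small groups: about 2, 4, 5.5 and 10 subjects at 75, 225, 675 and 1500 mg under the Appendix 2 rates.
2. Each exposure is divided by its own dose before the ratio is taken. This keeps all subjects but relies on dose linearity. It is within about 0.5% at a 4-day half-life and reads increasingly low at longer ones: about 3–4% at 7 days and 13–16% at 14 days.

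If the data presentation plan or the sponsor's PK document already covers the indices in escalated subjects, a cross-reference is enough. Only SAP wording changes; no new data are needed.

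Two editorial points can be corrected in the same edit. SAP 7.7 groups Ctrough by current dose and 7.7.2 by previous dose; this differs only for the Day 57 pre-dose sample in escalated subjects, and the two sections should agree. SAP 7.7.3 speaks of removing responders where escalated subjects, the non-responders, are meant.

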7.7.2 Ctrough Summary

Ctrough will be listed for all available data and summarized on day 15, 29, 43, 57, 71, and 85 for each group decided by previous dose.

7.7.3 Dose Proportionality

Dose proportionality will be provided separately for C_{max} and AUC(TAU) on study day 1 and 71 using a power model. Particularly, subjects going through dose escalation will be removed from the proportionality analysis for day 71. With the expected response rate of between 20% - 50% for 75mg, 225mg and 675mg, there would still be enough subjects left for the proportional analysis on day 71 after responders are removed. All subjects of 1500mg cohort will be included. In case there is no subject (all of the subjects are non-responders), or there are very few subjects (e.g., less than 3 subjects) in both 75mg and 225mg groups, dose proportionality analysis will not be provided for day 71. Decision will be data driven. Analysis results on day 71 will be discussed in the CSR if available; otherwise results on day 1 will be discussed.

The power model was described by Gough et al,¹

$$\text{PK Parameter} = A * \text{Dose}^{\beta}$$

Parameter of the above model, β , will be estimated by the simple linear regression of the natural log of the PK Parameter on the natural log of Dose:

$$E[\log(\text{PK Parameter}) | \text{Dose}] = \alpha + \beta * \log(\text{Dose}).$$

For each PK parameter, the point estimate of slope β and its 90% CI will be provided. In addition, the estimated regression line will be overlaid on the individual points in the corresponding scatter plot (log-log scale).

A slope (β) equal to 1 would indicate perfect dose proportionality. However, as the study is neither optimally designed nor powered to confirm the presence or absence of meaningful departures from dose proportionality, these results should be interpreted with caution.

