- Extremely small probability for β_2 being negative

It is assumed that the response rate at dose of 75mg, 225mg, 675mg, and 1500mg to be 0.2, 0.4, 0.55 and 0.7 respectively. A linear regression using the above data will give prior mean μ to be (-1.33, 0.72) with rounding error. The second and third bullets of the guidelines would make the stand deviation of β_1 to be 0.45, and β_2 to be 0.2. Prior distributions of β_1 and β_2 are assumed to be independent. A 95% credible interval of response rates under prior and without observation data is shown in Figure 1, where the top curve is the upper 97.5% quantile, the center is the mean, and the bottom is the lower 2.5% quantile. The circles represent the expected response rates at the selected doses. It can be seen that the chosen prior would lead to a mean response rate estimate being very close to the expected or assumed, and at the same time the wide region of 95% credible interval indicates that the prior's weak impact on the posterior estimation of response rate when data are observed.

Figure 1: 95% Credible Interval of Response Rate under Prior Only

Special consideration for titration

Non-responders at each cohort other than the maximum 1500mg cohort would be administered higher dose with the hope of becoming responders. Therefore, two response status data may be observed for those non-responders. Due to relative small sample size of each cohort, making use of status data after the titration dose is believed to increase the accuracy of model-based prediction under some reasonable assumptions. Listed in the below are two assumptions used in the adaptive dose selection:

- If a subject responds to a dose, the subject would respond to higher dose with probability 1.

- If a subject does not respond to a dose after 3 administrations, additional dosing at the same dose would not make a subject change from non-responder to responder.

Based on the above assumptions, a new approach is proposed to combine the subjects at two adjacent cohorts to estimate the response rate at the higher dose which is shared by the two cohorts.

Simulation

Trial simulation is done to show the performance of logistic regression and Bayesian logistic regression with starting dose data only or with titration data included. The Settings of simulation parameters are listed below for convenience:

[figure not shown]
- Doses: 75, 225, 675, 1500
- Rate: 0.2, 0.4, 0.55, 0.7

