2 STUDY DESCRIPTION

2.1 Study Design

This is a Phase 1b/2, multicenter, open-label, MAD study to evaluate the safety, efficacy, dose response, and pharmacology (PK, target engagement and PD) of BMS-986004 administered every 2 weeks in subjects with ITP.

Figure 2.1-1: Study Design Schematic

[figure not shown]
The study is divided into screening (3 weeks), response phase (6 weeks), remission phase (6 weeks) and follow up period (4 weeks). Forty subjects are treated in 4 dose panels, 75mg, 225mg, 675mg, and 1500mg, of 10 subjects each. BMS-986004 will be administered on day 1, 15, 29, 43, 57, 71, 85, a total of 7 doses as IV infusion. Four (4) doses will be administered during the Response Phase over a 6 week treatment period. The remaining 3 doses will be administered during the Remission Phase of the study over a 6 week treatment period. The study design schematic is presented in Figure 2.1-1.

Cohort of lower than 75mg or intermittent dose may be opened.

Intra-subject dose escalation

Subject may be dosed at a higher dose beginning from day 57 for the remainder of the study if clinically significant response has not been achieved at Day 43 and Day 50, and a favorable safety profile is observed.

Figure 2.1-2: Decision Rule on Intra-Subject Dose Escalation

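### SAP 7.7.3 excludes the escalated non-responders from the Day 71 dose-proportionality model but defends its size as if responders were excluded; about 2 of 10 subjects would remain at 75 mg

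*SAP*

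**What the plan says.** The design has four panels: "Forty subjects are treated in 4 dose panels, 75mg, 225mg, 675mg, and 1500mg, of 10 subjects each" (SAP 2.1). From Day 57 a subject may receive a higher dose "if clinically significant response has not been achieved at Day 43 and Day 50, and a favorable safety profile is observed" (SAP 2.1). SAP 7.7 says that "non-responders in each treatment group other than the 1500mg group will be dose-escalated to the starting dose of the next higher treatment group".

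The exclusion is stated twice. SAP 7.7 says "dose proportionality analysis will be provided by excluding subjects who have dose escalation on day 57", and SAP 7.7.3 says "subjects going through dose escalation will be removed from the proportionality analysis for day 71". The next sentence of 7.7.3 cites an expected response rate of 20% to 50% at the three lower doses and concludes that "there would still be enough subjects left for the proportional analysis on day 71 after responders are removed".

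The same paragraph keeps the whole 1500 mg cohort. It cancels the Day 71 analysis if there are no subjects, or very few (fewer than 3 is its example), in both the 75 mg and 225 mg groups. Day 71 results are discussed in the report if available, otherwise Day 1 results. The section asks for cautious interpretation because the study is not designed or powered for this question.

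SAP 7.7.1 summarises Day 71 PK by current dose, pooling escalated and non-escalated subjects. Steady state is expected by then, so "the PK parameters are considered to be related to the current dose, regardless of the previous doses".

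**The concern.** The rule and its justification name opposite groups. The escalated subjects are the non-responders, so responders are the ones kept. The SAP confirms this when it describes an empty group as one in which every subject is a non-responder.

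The difference matters because the expected response rate is lowest at 75 mg, the end of the dose range with most leverage on the slope. The justification describes a 75 mg group that is nearly intact, whereas the rule leaves a small remnant selected for having responded. The Day 71 slope, which the report prefers over Day 1, would then depend heavily on about two people. The SAP gives no reason for setting aside, in 7.7.3, subjects whom 7.7.1 accepts as informative about their current dose.

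**Working it through.** The SAP gives no number remaining, only the word enough, so there is no plan figure to reproduce.

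**Inputs.** There are 10 subjects per cohort (SAP 2.1). Protocol Appendix 2 assumes a "response rate at dose of 75mg, 225mg, 675mg, and 1500mg to be 0.2, 0.4, 0.55 and 0.7", in that order. The SAP's 20% to 50% range gives the same 2 of 10 at its lower end.

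**1. Expected number remaining of 10.** Under the rule this is 10 × p. Under the justification sentence it is 10 × (1 − p).

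| Dose | p | Rule (responders kept) | Sentence (responders removed) |
|---|---|---|---|
| 75 mg | 0.20 | 2.0 | 8.0 |
| 225 mg | 0.40 | 4.0 | 6.0 |
| 675 mg | 0.55 | 5.5 | 4.5 |
| 1500 mg | all kept | 10 | 10 |
| Total | | 21.5 | 28.5 |

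The two readings agree only at p = 0.5.

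**2. Chance of very few subjects.** With X ~ Binomial(10, p), P(X ≤ 2) is 0.678 at 75 mg, 0.167 at 225 mg and 0.027 at 675 mg. At 75 mg, P(X = 0) = 0.8^10 = 0.107.

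**3. Chance that the SAP's rule cancels Day 71.** Both lower groups must have fewer than 3. At 0.2 and 0.4 this is 0.678 × 0.167 = 0.113. If both rates were 0.2 it is 0.678² = 0.459.

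**4. Slope precision.** For the log-log regression, SE(slope) = sigma/√Sxx, with Sxx = Σ nᵢ(xᵢ − x̄)² and x = ln(dose) = 4.317, 5.416, 6.515, 7.313. The 5.5 at 675 mg is rounded to 6.

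- *Rule as written, 2/4/6/10:* x̄ = 6.478. The terms are 9.337 + 4.512 + 0.008 + 6.973, so Sxx = 20.83 and SE = 0.219 sigma. The two 75 mg subjects supply 9.337/20.83 = 45%.
- *All subjects by current dose:* 2 at 75 mg, 4 + 8 = 12 at 225 mg, 6 + 6 = 12 at 675 mg, 10 + 4 = 14 at 1500 mg. x̄ = 6.355. The terms are 8.301 + 10.573 + 0.307 + 12.861, so Sxx = 32.04 and SE = 0.177 sigma.
- *Comparison:* the information ratio is 32.04/20.83 = 1.54, and the SE is 19% smaller. Rounding 5.5 down to 5 instead gives a ratio of 1.58.
- *Reference:* a full 10 per cohort would give 0.140 sigma.

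**5. Is the steady-state premise plausible?** Protocol 3.3.1 equates 5 half-lives with 20 days, so one half-life is about 4 days. From the last lower dose (Day 43) to Day 71 is 28 days, or 7 half-lives, leaving 2⁻⁷ = 0.8% of it. The Day 71 dose is the second at the higher level. In a one-compartment model (assumption) the carry-over per 14 days is 2^(−14/4) = 0.088. Exposure relative to steady state is then (1 + 0.088)/(1/(1 − 0.088)) = 0.99.

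**6. Selection, if response is related to exposure.** This is an assumption: normal log exposure with SD sigma, and correlation rho with the latent response. Mean log exposure, in units of rho × sigma, is φ(z)/p for responders (1.40, 0.97, 0.72 at the three lower doses) and −φ(z)/(1 − p) for non-responders (−0.35, −0.64, −0.88). Here the unrounded expected counts are used.

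- *Not-escalated subset:* group means 1.40, 0.97, 0.72, 0. Expected slope bias is −0.48 rho × sigma.
- *Pooled by current dose (2/12/11.5/14.5):* group means 1.40, 0.09, 0.01, −0.27. Expected slope bias is −0.32 rho × sigma.

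Pooling therefore leaves 0.32/0.48, or about two-thirds, of any such bias.

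**The case against.** The best defence is that the operative rule is not in doubt. SAP 7.7 and the empty-group wording in 7.7.3 both show that non-responders leave, so a programmer would code it correctly and only one word is wrong. That stands for the coding. It does not save the claim about numbers, because 20% of 10 is 2 whichever word is used.

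It is also fair that about 21 subjects over a 20-fold dose range can estimate a slope, that the SAP sets no precision target, and that it advises caution and has a Day 1 fallback free of this exclusion. Restricting the model to subjects on one constant dose is a defensible wish, since it avoids relying on steady state, although the SAP does not offer that reason. These points limit the impact. They do not make the justification correct.

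A reader might infer several stronger things that the documents do not support:

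- *That Day 71 will probably be cancelled.* The 0.68 applies to 75 mg alone, and the rule needs both lower groups to be very small.
- *That even fewer would remain because the escalation criterion is stricter than R.* It is not uniformly stricter. At a baseline of 28,000/mm³, a count of 50,000 meets the escalation criterion's response definition (at least 50,000 with a rise of at least 20,000) but not the doubling to 56,000 that R requires. Above a baseline of 25,000 the order reverses. The documents also do not say which definition the 20% to 50% uses, and non-responders not escalated for safety reasons would stay in.
- *That the slope is biased.* Nothing in the documents shows that response is related to exposure. This is a risk, not a finding.
- *That pooling repairs the 75 mg group.* It does not. That group still has about 2 subjects, all responders.

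**Conclusion.** The justification in SAP 7.7.3 is wrong as written and remains unsupported at 75 mg once the word is corrected. At the documents' own rates, about 2/4/5.5 of 10 subjects remain at the three lower doses, with a 0.68 chance of fewer than 3 at 75 mg. The analysis would usually still run (cancellation about 11%, or 46% if both lower rates are 0.2), but with a slope SE of 0.219 sigma and about 45% of the information from some two subjects.

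These figures assume that the Appendix 2 rates apply to the criterion that drives escalation, that every non-responder below 1500 mg is escalated, and that nobody drops out. The consequence is confined to a descriptive analysis of secondary PK endpoints. The documents tie no dosing, safety or efficacy decision to the Day 71 slope. It should be corrected because the contradiction is plain and the remedy is cheap.

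**What to change.** In SAP 7.7.3:

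1. Correct the sentence so that it says non-responders (the escalated subjects) are removed, and replace the word enough with the expected number remaining at each dose (about 2, 4, 5.5 and 10).
2. Fit the Day 71 power model to all subjects by current dose, consistent with SAP 7.7.1, and amend the matching exclusion in SAP 7.7.
3. Report the not-escalated subset as a sensitivity analysis.
4. State the limits of the pooled analysis: it relies on steady state by Day 71, it adds no subjects at 75 mg, and it reduces but does not remove possible selection by response.

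The cost is SAP wording and one additional model fit. It needs no new data and no change to dosing or study conduct. The gain is about 1.5 times the information on the slope.
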